5.3. Lifestyle Considerations

Prolonged exposure to natural or artificial sources of UV radiation (including sun lamps, tanning booths, etc) is prohibited from 2 weeks prior to the baseline visit through the last study visit. When outdoors, participants will be advised to wear loose-fitting clothing that protects the treated areas from the sun.

If sunscreen, makeup, or other cosmetics have been applied to the areas to be treated, participants should wash the treatment areas with mild soap and water and pat dry before application of study cream. See Section 6.6.1 for additional guidance.

Participants should abstain from physical activity that can cause significant sweating for approximately 2 hours following study cream application.

Swimming during the CT period of the study is not recommended. If unavoidable, it is recommended that swimming should not take place within 2 hours before and after study cream application.

5.4. Screen Failures

Screen failures are defined as participants who consent to participate in the clinical study but are not subsequently entered in the study.

Tests with results that fail eligibility requirements may be repeated once during screening if the investigator believes the result to be in error. Additionally, a participant who fails screening may repeat the screening process 1 time if the investigator believes that there has been a change in eligibility status. Participants who rescreen must reconsent (if rescreened ≥ 28 days after the initial screening or ≥ 35 days after the initial screening for those participants on prior medications requiring a 4-week washout period, as described in Section 5.2, Exclusion Criterion 5b) and be assigned a new participant number.

5.5. Replacement of Participants

Participants are not anticipated to be replaced during the study. However, as noted in Appendix B, due to the evolving situation of the COVID-19 pandemic, the sponsor may decide to recruit additional participants in the study beyond the expected number (eg, if a substantial number of participants withdraw early from the study).

6. STUDY TREATMENT

6.1. Study Treatment Administered

Table 6 presents the study treatment information.

Table 6: Study Treatment Information

Study Treatment Name:	Ruxolitinib
Dosage Formulation:	Cream
Unit Strength:	1.5%
Route of Administration:	Topical
Administration Instructions:	BID. A thin film is applied to areas affected by AD in the morning and in the evening at least 1 hour before bedtime.
Packaging and Labeling:	Ruxolitinib cream will be provided in 60-g tubes. Each tube will be labeled as required per country requirements.
Storage:	Ambient (15°C-30°C/59°F-86°F)
Status of Treatment in Participating Countries:	Approved in the USa; investigational in all other countries

^a Opzelura (ruxolitinib) cream.

Ruxolitinib cream study drug will be supplied in 60-g tubes and applied topically as a thin film BID (optimally at equal intervals, eg, ideally 12 hours apart but with at least 8 hours between applications) to the affected areas in the morning and in the evening, with the evening application at least 1 hour before bedtime.

At the baseline visit, an estimate of the %BSA to be treated will be used by the IRT system to calculate the number of tubes of study cream to be dispensed. All AD areas identified at the baseline visit should continue to be treated through the end of the CT period (at Week 8), even if the area begins to improve or the AD resolves completely, unless the participant meets any criteria for stopping study cream.

If there are new areas to be treated, including expansion of existing areas or development of new areas, after consultation with the investigator, and if there are no safety concerns, study cream should be applied to these areas in addition to the areas identified at the baseline visit (up to a maximum total of 20% BSA) for the remainder of the CT period, and the percentage of BSA to be treated will be recalculated and increased accordingly. This new estimate will be entered into the IRT system to calculate the number of tubes of study cream to be dispensed. Approval to treat these additional areas may occur via telephone, although the investigator, at their discretion, may ask the participant to return for an unscheduled visit. This is a close reflection of the clinical practice of managing AD in the outpatient setting. During the CT period, participants whose additional new areas to be treated in addition to the areas identified at the baseline visit exceed 20% BSA should be discontinued from study cream and complete the ET assessments.

During the LTS period (ie, starting at the Week 8 visit), participants will have study visits at Week 12 and then every 8 weeks until the end of the study (44 weeks total), with the final possible application being the evening application on the day before the Week 52 visit. At each

LTS period visit, AD lesions will be evaluated by the investigator to confirm whether the participant requires continuation of therapy (total IGA score \geq 1) or can (re)enter the observation/no treatment cycle (total IGA score = 0). During the LTS period, only areas with active disease need to be treated. Participants who develop new or expanded areas of AD may treat these additional areas with approval by the investigator as long as the total treated BSA does not exceed 20% and there are no safety concerns regarding the additional application of study cream. Approval to treat additional areas may occur via telephone, although the investigator, at their discretion, may ask the participant to return for an unscheduled visit.

The start and end dates of treatment applications will be captured by the participant. Once the lesions clear, participants should continue to apply study cream for an additional 3 days to the areas of the body where lesions were last present before discontinuing treatment. If during this 3-day window the participant attends a study visit and the total IGA score is 0 at that visit, as assessed by the investigator, treatment is to be stopped. The date of the study visit will be recorded as the treatment cycle end date. If a lesion recurs, then treatment should be resumed at the first sign of recurrence.

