6.1.1. Study Treatment Application Guidance

Participants should remove study cream from the tube and apply the study cream with their fingertip in small amounts until all of the areas to be treated are covered by a thin, even film (see Figure 2).

Figure 2: Study Cream Application Using a Fingertip

Source: DermNet New Zealand (www.dermnetnz.org).

On the day of a visit, study cream will be applied in the clinic during the visit, under direct supervision of the site staff. The tube will be weighed before and after application to determine the participant's usage.

The Day 1 (baseline) visit should take place in the morning, so that the initial dose of study cream is applied in the clinic in the morning. For all other visits, the participant may apply either of the 2 daily doses at the site, as long as it is at least 4 hours since the previous dose was applied (see Section 8.4). Note that no study cream will be applied at any of the visits from Week 8 to Week 52 if the IGA is 0 (ie, no active AD lesions) or at the ET visit.

Application instructions will be provided by the site study staff, and the participants will record their daily applications via an eDiary. Participants must not apply study cream more often than

BID and should limit use to no more than one 60-g tube per week. Refer to the Study Manual for participant instructions for handling study cream.

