8.1.4. Distribution of Reminders and eDiaries

Starting at the Day 1 visit, each participant will use a study cream—specific eDiary in order to record use of the study cream. The completed eDiary will be reviewed during each of the participant's study visits and data will be confirmed by the study staff.

Qualified clinical study staff will review the participants' entries for compliance, as outlined in Section 6.4.

Participants will be provided with a reminder starting on Day 1 and at all CT and all LTS visits through Week 48. The reminder will indicate the date and time of the next visit and will also remind the participant that their morning application of study cream will be take place at the clinic under site supervision after blood or saliva collection for PK and safety evaluations have been completed.

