8.4. Pharmacokinetic Assessments

Pharmacokinetic blood and saliva samples will be collected from all participants at the visits and collection times shown in the SoA (see Table 3 [CT period] and Table 4 [LTS period]) and as noted in Table 10.

The exact date and time of the PK blood and saliva sampling and the date and time of the last application of study cream preceding the blood or saliva sample (if applicable) will be recorded in the eCRF.

Instructions for sample preparation and shipping will be provided in the Laboratory Manual. Participants will receive reminders in advance of the study visit providing instructions to hold the application of study cream on the day of the visit and to record the time of the prior application of study cream.

Blood samples for PK must be drawn from an area that has not been treated with study cream, or if that is not possible, the participant must not apply study cream from the previous application of study cream on the immediate body area where blood is to be drawn (ie, for site visits in the morning, this means the application on the evening before [second dose of that day]; for site visits in the afternoon this means the application on the morning of the same day [first dose of that day]).

If blood is drawn from an area that has been treated with study cream, the site personnel must document the missed application at the location of the blood draw in the eCRF. After the PK blood or saliva sample is collected, participants will apply ruxolitinib 1.5% cream.

All analyses will be conducted by Incyte Corporation (Wilmington, DE) or Incyte's designee.

Table 10: Pharmacokinetic Blood and Saliva Sample Timing

Study Visit	Timing of Sample
CT period	Samples will be collected at any time prior to study cream application during study visits, but must be at least 4 hours after the previous application of study cream and after assessment of vital signs during the visit:
	Blood and saliva samples
• Week 2	Blood and saliva samples
• Week 4	Saliva sample only
• Week 8/EOT1 or ET	
LTS period: Weeks 12, 20, 28, 36, 44, and 52/EOT2	Saliva samples will be collected at any time prior to study cream application during study visits, but must be at least 4 hours after the previous application of study cream and after assessment of vital signs during the visit. No blood samples will be collected during the LTS period.

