APPENDIX C. PROTOCOL AMENDMENT SUMMARY OF CHANGES

Document	Date
Amendment 1	30 NOV 2022

Amendment 1 (30 NOV 2022)

Overall Rationale for the Amendment

The primary purpose of this amendment is to clarify that Day 1 serum chemistry and hematology testing will be performed only if the screening laboratory test date is more than 2 weeks before Day 1. Additional changes and clarifications are summarized below.

1. Section 1, Protocol Summary (Table 3: Schedule of Activities: Continuous Treatment Period; Table 4: Schedule of Activities: Long-Term Safety Period); Section 6.1.1, Study Treatment Application Guidance; Section 8.4, Pharmacokinetic Assessments (Table 10: Pharmacokinetic Blood and Saliva Sample Timing)

Description of change: Removed the requirement for all morning study cream applications to be performed at the site, and revised to allow participants to apply either of the 2 daily doses at the site after Day 1.

Rationale for change: To allow flexibility in appointment time and to ease the burden on the participant and/or legal guardian.

2. Section 1, Protocol Summary (Table 3: Schedule of Activities: Continuous Treatment Period); Section 8.3.5, Laboratory Assessments

Description of change: Updated to clarify that Day 1 testing for serum chemistries and hematology will only be performed if the interval between Day 1 and the date of the screening laboratory tests is great than 2 weeks.

Rationale for change: To clarify when Day 1 testing is required.

3. Section 1, Protocol Summary (Table 3: Schedule of Activities: Continuous Treatment Period; Table 4: Schedule of Activities: Long-Term Safety Period)

Description of change: Added an assessment for Itch NRS eDiary compliance.

Rationale for change: To improve compliance of Itch NRS eDiary assessments.

4. Section 1, Protocol Summary (Table 3: Schedule of Activities: Continuous Treatment Period); Section 8.4, Pharmacokinetic Assessments (Table 10: Pharmacokinetic Blood and Saliva Sample Timing)

Description of change: Revised the timing of the PK blood draw from morning to any time prior to study drug application but at least 4 hours after the previous application of study cream. Also, provided guidance on blood draws from treated areas if no other acceptable blood draw areas are available.

Rationale for change: To decrease participant burden by allowing flexibility in the appointment time and minimize missed PK assessments.

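### SAP 8.1 summarises LTS saliva concentrations as troughs without separating participants who are off cream at the visit

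*Protocol*

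**What the plan says.** Trough ruxolitinib concentration at each postbaseline visit is a secondary endpoint (Protocol Table 5, SAP Table 1).

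**Regimen.** Protocol 6.1 sets the routine application interval: "ideally 12 hours apart but with at least 8 hours between applications". In the LTS period only active lesions are treated. Under Protocol 6.1 and 8.2.3, a total IGA of 1 or more means treatment, and a total IGA of 0 moves the participant into an observation cycle without cream.

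**Sampling.** Protocol 8.4 states: "Pharmacokinetic blood and saliva samples will be collected from all participants at the visits and collection times shown in the SoA". Table 10 schedules saliva at Weeks 12, 20, 28, 36, 44 and 52 and requires that a sample "must be at least 4 hours after the previous application of study cream and after assessment of vital signs during the visit". It gives no upper limit. The date and time of the sample, and of the last application where there is one, go into the eCRF.

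**Analysis.** SAP 8.1 summarises trough plasma at 2 CT visits, and trough saliva at 3 CT visits and 6 LTS visits, by visit. It also averages saliva within each participant by period. It sets no condition on treatment status and makes no use of time since last application. The PK-evaluable population (SAP 5.3.2) requires one application at any time and one postbaseline sample.

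**The concern.** A trough is a measure of exposure on treatment. A sample from a participant who stopped cream days or weeks before the visit measures washout. SAP 8.1 puts both kinds of sample under one label.

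Two reported results are affected. The LTS visit mean falls as more participants are clear and off cream, so a change over visits could reflect disease control rather than absorption. The LTS individual mean averages on-treatment and off-treatment visits of the same person, so it partly measures how often that person was treated. A reader comparing CT with LTS saliva could take the difference as lower systemic exposure during treatment. In a post-marketing safety study, that is the direction in which one would least want an unexplained shift.

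The exploratory concentration and hematology plots (Protocol 10.4.5) could inherit the problem if they use LTS saliva. Off-treatment participants would then share the lowest quartile with treated participants who absorb little.

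A lesser point concerns plasma as well as saliva. Sampling is allowed from 4 hours after an application with no ceiling, so time since last application can differ between samples, and the SAP does not account for it.

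**Working it through.** The plan gives no figure on this point to reproduce. The check is a comparison of texts, followed by arithmetic on stated assumptions.

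**1. Can an off-treatment sample enter the summary?**
- Protocol 8.4 samples all participants. The saliva row of Table 4 excludes the early termination visit but has no treatment condition. The clinic application row of the same table is limited to participants with active lesions.
- Protocol 8.8.1 expressly foresees participants who have been clear and off cream from Week 48 or earlier until Week 52. At the Week 52 visit, where saliva is scheduled, they have had at least 52 − 48 = 4 weeks without cream.
- SAP 5.3.2 and 8.1 contain nothing that removes or separates these samples. A participant who applies no cream at all in the LTS period still qualifies as PK evaluable.

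So off-treatment samples are expected, and the analysis includes them.

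**2. Which samples are meant?** An IGA of 0 at the visit is not enough. Protocol 6.1 has participants continue for 3 days after clearing, so a participant found clear at the visit may have applied cream the evening before. The issue is participants who arrive already in an observation cycle.

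**3. Effect on the visit mean.** Let M be the mean on-treatment trough, q the share of samples taken off treatment, and r the off-treatment concentration as a fraction of M.

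Visit mean = (1 − q)M + q·r·M = M[1 − q(1 − r)].

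With r near 0 (assumed) this is (1 − q)M:

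| q (assumed) | Visit mean relative to M | Fall |
|---|---|---|
| 0.10 | 0.90 | 10% |
| 0.25 | 0.75 | 25% |
| 0.50 | 0.50 | 50% |

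Any residual concentration reduces the fall to q(1 − r). These figures apply to the arithmetic mean; medians and geometric means would move by other amounts.

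**4. Effect on the individual LTS mean.** For a participant on treatment at k of 6 LTS visits, with the same on-treatment trough each time:

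Period mean relative to on-treatment trough = [k + (6 − k)r]/6, which is k/6 when r is near 0.

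| k | 5 | 4 | 3 | 2 | 1 |
|---|---|---|---|---|---|
| k/6 | 0.83 | 0.67 | 0.50 | 0.33 | 0.17 |

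**5. Time since last application.** Table 10 sets a floor of 4 hours. For blood draws at afternoon visits, Protocol 8.4 describes the preceding application this way: "for site visits in the afternoon this means the application on the morning of the same day [first dose of that day". For morning visits it is the evening before. Two samples at the same visit can therefore differ by hours in time since dose. Week 52 is an exception to the early case, because Protocol 6.1 makes the evening before that visit the last possible application. The documents give no half-life or absorption profile, so no size can be attached.

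**The case against.** The strongest counter-argument is that LTS treatment is as-needed by design. A summary over all participants then describes exposure under the regimen as used, while a summary of treated participants answers a different question, conditional on active disease. This stands, and it is the reason to keep the all-sample summary. It does not justify calling that summary a trough.

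Other points limit the scope, and they also stand. No blood is drawn in the LTS period. In the CT period all baseline lesions are treated even if they clear. SAP 8.1 averages saliva by period, so CT means are not mixed with LTS means. Protocol 10.4.3 allows further summaries, and the listings in SAP Appendix A include a heading for data excluded from PK analyses. Exclusions are therefore possible, but no rule is stated, and they would be chosen after the concentrations are known.

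A reader might infer four stronger things that the documents do not support.
- *That the protocol contradicts itself on 8 versus 4 hours.* Protocol 6.1 gives the routine interval. Protocol 6.1.1, a subsection of it, gives the visit-day rule, under which the clinic dose is allowed "as long as it is at least 4 hours since the previous dose was applied". Amendment 1 gives its reason for the matching PK sampling rule: "To decrease participant burden by allowing flexibility in the appointment time and minimize missed PK assessments".
- *That trough sampling has no lower limit.* Table 10 sets 4 hours, and SAP 3.4 defers to the protocol for procedures.
- *That late samples are built in.* Protocol 8.4 mentions "instructions to hold the application of study cream on the day of the visit", and Protocol 8.1.4 places the morning application "at the clinic under site supervision after blood or saliva collection for PK". Taken alone, these could put an afternoon sample long after the previous evening's dose. But the afternoon-visit text in 8.4 expects a dose that morning, and 8.1.4 reads as a morning-visit instruction. Late samples are possible, but they are not the course described.
- *That the size of the distortion is known.* It is not.

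**Conclusion.** The concern holds for LTS saliva. As written, SAP 8.1 would report off-treatment values as troughs, both by visit and in the individual LTS means. If off-treatment concentrations are below on-treatment ones, the reported values are lower than the on-treatment trough. Under the near-zero assumption the visit mean falls by the share off treatment, and an individual mean falls to k/6 of the on-treatment value. The documents give neither that share nor the residual concentration, so these figures illustrate a mechanism and do not estimate a bias.

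Variation in time since last application, in plasma and saliva, is a secondary point of unknown size.

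The consequence is limited to a descriptive secondary endpoint and possibly some exploratory plots. No hypothesis is tested on these data, and the primary analysis of treatment-emergent adverse events is unaffected. This is a cheap improvement to consider.

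**What to change.** Change SAP 8.1 only; visit scheduling and the protocol stay as they are.

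1. Derive time since last application from the eCRF times, and treatment status from those times and the recorded cycle start and end dates. Count a sample as on treatment if the participant was in a treatment cycle and had applied cream in that cycle before the sample. A cycle that starts at the clinic after sampling does not count, and IGA at the visit should not be used as the criterion.
2. Report LTS saliva trough, by visit and as individual means, for on-treatment samples. Show off-treatment samples separately, with their number at each visit, and keep the all-sample summary.
3. Plot or list plasma and saliva concentration against time since last application.
4. Flag off-treatment samples in any Protocol 10.4.5 grouping that uses them.

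A fixed time window as the main basis for the trough summary is not needed; whether to add one is the sponsor's choice.

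The cost is a SAP paragraph, one figure or listing and a modest amount of programming. No new data are needed. The downside is fewer samples in the on-treatment LTS summary, which then describes currently treated participants only. The retained all-sample summary covers the rest.

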6.1.1. Study Treatment Application Guidance

Participants should remove study cream from the tube and apply the study cream with their fingertip in small amounts until all of the areas to be treated are covered by a thin, even film (see Figure 2).

Figure 2: Study Cream Application Using a Fingertip

Source: DermNet New Zealand (www.dermnetnz.org).

On the day of a visit, study cream will be applied in the clinic during the visit, under direct supervision of the site staff. The tube will be weighed before and after application to determine the participant's usage.

The Day 1 (baseline) visit should take place in the morning, so that the initial dose of study cream is applied in the clinic in the morning. For all other visits, the participant may apply either of the 2 daily doses at the site, as long as it is at least 4 hours since the previous dose was applied (see Section 8.4). Note that no study cream will be applied at any of the visits from Week 8 to Week 52 if the IGA is 0 (ie, no active AD lesions) or at the ET visit.

Application instructions will be provided by the site study staff, and the participants will record their daily applications via an eDiary. Participants must not apply study cream more often than

BID and should limit use to no more than one 60-g tube per week. Refer to the Study Manual for participant instructions for handling study cream.

